3.3. Patient Selection Criteria

Subjects who currently consented and enrolled in the PFBHS protocol, can tolerate PET scan procedures, and have the ability to provide informed consent for study procedures will be provided opportunity to participate this study.

Refer to Protocol Section 5.3, Selection of Subjects, for the detail of inclusion/exclusion details.

4. STUDY DURATION AND VISIT SCHEDULE

The study participants will have a screening visit and two imaging visits. The details of these visits are shown below.

Table 2: Visit Schedule

Evaluations	Screening Assessments ^a	Flortaucipir Imaging Visit	End of Flortaucipir Imaging (prior to discharge)	Follow-up Phone Call ^b	Florbetapir Imaging Visit ^c	End of Florbetapir Imaging (prior to discharge)	Follow-up Phone Call ^b
Signed Informed Consent	X						
Demographics	X						
Medical History	X						
Concomitant Medications	X						
Vital Signs	X ^d	X ^{e, f}	X ^g		X ^c		
Clinical Lab Tests	X ^h						
ECG	X ⁱ						
MMSE, Beck Depression Inventory II, Digit span forward/backward	X						
MRI	X ^j						
PET Brain Scan		X ^{k, l}			X ^{m, n}		
Evaluation by a physician	X	X ^o	X ^o		X ^p	X ^p	
Adverse Events	X	X	X	X	X	X	X
Serious Adverse Events	X	X	X	X	X	X	X

- Screening may take place over several days. All assessments must be performed within 90 days prior to the ¹⁸F-AV-1451 imaging session. Subjects may be permitted to return for the ¹⁸F-AV-1451 PET scan after the 90 day window with sponsor approval if the investigator does not recognize any significant medical changes.
- A follow-up phone call to the subject, or information where applicable, will be conducted within 2 or 3 business days of each imaging day, but not before 48 hours post-injection, to confirm subject well-being and to collect information about any new adverse events. If both of these days are not business days, the follow-up phone call can occur the following business day.
- For all professional fighters ≥ 50 years of age and other participants in whom, and in the opinion of the investigator, the clinical presentation suggests a possible diagnosis of AD.
- Screening vital signs include pulse rate, respiratory rate, supine blood pressure, height and weight.
- Vital signs (pulse, respiratory rate, supine blood pressure) and weight will be taken prior to dose administration.
- Vital signs (pulse, respiratory rate, supine blood pressure) will be taken within 5 minutes after completion of injection of dose administration.
- Vital signs (pulse, respiratory rate, supine blood pressure) will be taken after completion of the PET scan prior to discharge.
- Safety labs to include hematology, chemistry and urinalysis including plasma thiamine (vitamin B1) level.
- ECG (with results reviewed prior to ¹⁸F-AV-1451 administration).
- If a volumetric MRI has not been performed as part of PFBHS within six months of the ¹⁸F-AV-1451 PET imaging visit, a volumetric MRI is to be performed as part of this study's screening assessments.
- Subjects will receive a single IV bolus injection target dose of 370 MBq (10 mCi) of ¹⁸F-AV-1451 Injection followed by a saline flush.
- At approximately 75 minutes following ¹⁸F-AV-1451 injection, a continuous 30-minute brain scan will begin.
- Subjects will receive a single IV bolus injection target dose of 370 MBq (10 mCi) of florbetapir followed by a saline flush.
- At approximately 50 minutes following florbetapir injection, a continuous 10-minute brain scan will begin.
- Or a licensed/credentialed medical professional (i.e. PET technologist, imaging center nurse or a regional equivalent) designated by the site principal investigator. If a designee performs this activity, the physician must be available to provide medical consultation.
- Or physician designee.

5. CLINICAL AND IMAGING ASSESSMENTS

5.1. Screening and Baseline Clinical Assessments

Subjects currently enrolled in the PFBHS protocol will be contacted to participate. Screening assessments may take place over several days, within 90 days of the flortaucipir PET scan, and will include:

- Informed Consent will take place before any ¹⁸F-AV-1451-A11 study procedures;
- Demographics (birth year, gender, race, ethnicity, education, alcohol, drug use and smoking);
- Medical history and concomitant medications;
- Safety assessments: Vital signs (pulse rate, respiratory rate, supine blood pressure, height and weight), electrocardiogram (ECG) (with results reviewed prior to flortaucipir administration), and safety labs (hematology, chemistry and urinalysis) including plasma thiamine (vitamin B1) level;
- Mini-Mental State Examination (MMSE);
- Digit span forward and backward;
- Beck Depression Inventory II;
- If a volumetric MRI has not been performed as part of PFBHS within six months of the flortaucipir PET imaging visit, a volumetric MRI is to be performed as part of this study's screening assessments; and
- A physician will see the subject during the screening assessments.

5.2. Imaging Assessments

5.2.1. Flortaucipir PET Imaging Visit

Subjects who qualify for the study will return to the clinic at a later date for the flortaucipir PET imaging visit. For the flortaucipir PET imaging visit, an intravenous catheter will be placed for IV administration of flortaucipir Injection.

- A physician or a licensed/credentialed medical professional (i.e., a PET technologist, imaging center nurse or a regional equivalent) designated by the site principal investigator must assess or evaluate the subject prior to administration of Flortaucipir Injection to determine if they are still suitable to undergo the scan. If a designee performs this activity, a physician must be available to provide medical consultation;
- Vital signs will be taken (pulse rate, respiratory rate, supine blood pressure) at the following time points:
 - Prior to administration of Flortaucipir Injection (weight will also be collected)
 - Within 5 minutes after completion of injection of Flortaucipir Injection
 - After completion of the PET scan prior to discharge;
- Subjects will receive a single IV bolus injection target dose of 370 MBq (10 mCi) of flortaucipir Injection followed by a saline flush.
- At approximately 75 minutes following injection, a continuous 30-minute brain scan will begin;
- The injection site will be observed for excessive inflammation or damage to the surrounding tissue where the dose was injected;

- AEs will be continuously monitored during the flortaucipir PET imaging visit. Subjects who experience an AE will not be discharged from the imaging center until the event has resolved or stabilized;
- A physician or a licensed/credentialed medical professional (i.e., a PET technologist, imaging center nurse or a regional equivalent) designated by the site principal investigator must assess or evaluate the subject prior to discharge from the imaging center to evaluate the subject's readiness for discharge. If a designee performs this activity, a physician must be available to provide medical consultation; and
- A follow-up phone call to the subject, or informant where applicable, will be conducted within 2 or 3 business days of the imaging day, but not before 48 hours post-injection, to confirm subject well-being and to collect information about any new AEs. If both of these days are not business days, the follow-up phone call can occur the following business day.

5.2.2. Florbetapir PET Imaging Visit

All professional fighters > 50 years of age and other participants in whom, and in the opinion of the investigator, the clinical presentation suggests a possible diagnosis of AD will return to the clinic for a florbetapir PET imaging visit. The PET imaging visits must be performed no more than 60 days apart.

- A physician, or physician designee, must see the subject prior to administration of Florbetapir Injection to determine if they are still suitable to undergo the scan;
- Vital signs will be taken (pulse rate, respiratory rate, supine blood pressure and weight) immediately prior to injection of florbetapir;
- Subjects will receive a single IV bolus injection target dose of 370 MBq (10 mCi) of florbetapir followed by a saline flush;
- At approximately 50 minutes following injection, a continuous 10-minute brain scan will begin;
- AEs will be continuously monitored during the florbetapir PET imaging visit. Subjects who experience an AE will not be discharged from the imaging center until the event has resolved or stabilized;
- A physician, or physician designee, will see the subject prior to discharge from the imaging center to evaluate the subject's readiness for discharge; and
- A follow-up phone call to the subject, or informant where applicable, will be conducted within 2 or 3 business days of the imaging day, but not before 48 hours post-injection, to confirm subject well-being and to collect information about any new AEs. If both of these days are not business days, the follow-up phone call can occur the following business day.

5.3. Post-Baseline Assessments

Besides the clinical assessments at screening visit and relative imaging assessments, there will be no post-baseline assessments in this study.

5.4. Final Evaluation or Premature Termination Visit

There will be only one clinical and imaging assessment visit in this study, and will not include any premature termination visit.

6. DEFINITIONS AND CONVENTIONS

6.1. Data Conventions

Data will be summarized using descriptive statistics (number of subjects [n], mean, standard deviation [SD], median, minimum (min), and maximum (max)) for continuous variables and using frequency count and percentage for discrete variables.

All analysis will be performed using SAS version 9.2 or higher.

6.2. General Summary Table and Individual Patient Data Listing Considerations

The tables and listings will be numbered using a decimal system to reflect main levels of unique tables and listings and sub-levels of replicate tables and the listings with two digits per level (e.g., Table XX.YY.ZZ...). Tables will be presented starting with 14 and individual patient data listings are presented starting with 16.

6.3. Calculations Using Dates

The date of study drug (flortaucipir) administration in this study will be considered relative day 1, and the day before the dose of study drug will be relative day -1. Relative days will be calculated as follows only when the full assessment date is known (i.e., partial dates will have missing relative days):

- For days on or after the first dose of study drug: (Assessment Date – Exposure Date) + 1.
- For days before the first dose of study drug: Assessment Date – Exposure Date

6.4. Visit Windows Relative to the First Dose of Study Medication

No visit windowing will be performed for this study.

7. ANALYSIS POPULATIONS

7.1.1. Enrolled Population

All subjects who meet the inclusion/exclusion criteria and have consented to be enrolled in this study, and have baseline data captured in the eCRF database will consist of the enrolled population.

7.1.2. Safety Analysis Population

The safety analysis population will consist of all subjects who received at least one injection of flortaucipir or florbetapir.

7.1.3. Efficacy Analysis Population

This population includes all subjects in safety population for whom valid image data are available for the flortaucipir visit(s). All primary and exploratory analyses will be based on this population.

8. DISPOSITION AND WITHDRAWALS

The entire enrollment population will be represented in the disposition table. The disposition table be reported overall and broken down by enrolling diagnosis and include a summary of:

- Total number of enrolled patients
- Total number of patients in safety population
- Number and percentage of completed patients (defined as completing scan procedure and receiving follow-up safety phone call)
- Number and percentage of patients in efficacy population
- Number and percentage of discontinued patients

The disposition table will also include details on discontinuation reasons:

- Adverse Event
- Death
- Lost to Follow-up
- Other
- Physician Decision
- Protocol Violation
- Study Terminated by Sponsors
- Technical Problems
- Withdraw by Subject

Efficacy, completed and discontinued percentages will be based on the safety population. Percentages outlining discontinuation reasons will be based on the number of discontinued subjects. Discontinued reasons will be presented in a table by descending total frequency.

9. BASELINE PATIENT DATA

9.1. Baseline Demographics and Characteristics

Demographic data and other baseline characteristics will be presented for the flortaucipir safety analysis population in a table.

The most recent value prior to a subject's initial injection of flortaucipir will be considered the baseline value, and will be reported in the demographics table. The following data from the will be reported in the baseline and demographics table:

- Age (years)
- Gender
- Race
- Ethnicity
- Highest Level of Education
- Alcohol use
- Tobacco use
- Recreational Drug Use
- Height (cm)
- Weight (kg)
- MMSE
- Beck Depression Inventory II
- Digit span forward/backward

9.1.1. Missing Baseline Data

No imputation will be performed on missing baseline demographic data.

9.2. Medical and Surgical History

Medical and Surgical History information will be presented for the safety analysis population. Medical and Surgical History will be coded using MedDRA Version 17. Medical History findings are defined as those conditions which stop prior to or at Screening.

Medical and surgical history will be presented in a listing including:

- System Organ Class (SOC)
- Condition/Disease
- Start Date
- End Date
- Condition Still Present (Y/N)

Medical and Surgical History data will be presented by System Organ Class (SOC) and Preferred Term (PT), sorted in descending frequency.

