7.7.2 Adverse Event Definitions

Adverse Events

An adverse event is any undesirable experience occurring to a subject during a clinical trial, whether or not considered related to the study drug.

For reporting purposes, Avid will distinguish among pre-existing conditions, trial-emergent adverse events and treatment-emergent adverse events.

Pre-existing conditions (i.e., undesirable experiences, signs or symptoms that begin prior to the Screening Visit) will be recorded on the medical history eCRF pages. During the study, site personnel will record any change in the condition(s) and occurrence and nature of any AEs. Signs and symptoms that are believed to be due to the pre-existing condition(s) (started prior to dose of study medication) do not have to be recorded in the AEs section of the eCRF, unless there is an increase in frequency and severity.

Trial-emergent adverse events are undesirable experiences, signs or symptoms that begin, or worsen in intensity or frequency, after the informed consent, and prior to administration of the study drug at the imaging visit. Adverse events that occur between the florbetapir F 18 and the ¹⁸F-AV-1451 PET scans outside the 48 hour windows will also be considered trial-emergent adverse events. These will be recorded on the adverse event eCRFs.

Treatment-emergent adverse events are any untoward medical occurrence associated with the use of a drug in humans, whether or not considered drug related. For the purposes of this study, untoward medical occurrences will be considered associated with the use of ^{18}F -AV-1451, and thus be reported as adverse events, if they occur within 48 hours after ^{18}F -AV-1451 administration. Untoward medical occurrences will be considered associated with the use of Florbetapir F 18 Injection, if they occur within 48 hours after Florbetapir F 18 Injection administration.

The end of study, for the purpose of adverse event reporting, is defined as 48 hours after the last study drug administration (^{18}F -AV-1451 or Florbetapir F 18 Injection).

Serious Adverse Event (SAE)

A SAE is an AE that results in one of the following outcomes or constitutes one of the following events:

- Death;
- Initial or prolonged inpatient hospitalization (other than that required by protocol; “social hospitalization” or any hospitalization for non-medical reasons does not constitute a SAE);
- A life-threatening experience (that is, immediate risk of dying);

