8. STATISTICAL ANALYSIS

8.1 General Statistical Considerations

All statistical analyses will be performed using SAS® version 8.2 or higher.

The study data collected under PFBHS protocol, such as but not limited to subjects’ demographic and baseline characteristics, history taking, neurological and behavioral evaluations, and MRI will be transferred to Avid for analysis purposes.

Data will be summarized using descriptive statistics (number of subjects [N], mean, standard deviation [SD], median, quartiles, minimum, and maximum) for continuous variables and using frequency count and percentage for discrete variables. The demographic and baseline characteristics data will be summarized for all subjects in the safety population according to clinical group. Safety data will be summarized for all patients.

Subject listings of all data from the eCRFs as well as any derived variables will be presented.

Descriptive Statistics will be applied to describe the ¹⁸F-AV-1451 uptake and florbetapir SUVR distribution by subject enrollment groups (active/retired professional fighters and cognitive impaired/normal). ANOVA test, or comparable non-parametric tests such as the Kruskal-Wallis test when ANOVA’s pre-requisites are not met, will be conducted to detect the differences

in ^{18}F -AV-1451 uptake measurements across the enrollment groups. If an overall difference is detected, then a two sample t-test, or Wilcoxon rank sum test when the pre-requisite of t-test is not met, will be applied to test if there are differences seen in ^{18}F -AV-1451 uptake measurements between pair-wised enrollment groups. Additional exploratory analyses will be applied to explore the relationship among ^{18}F -AV-1451 uptake measurements, cognitive and neurological measurements, and other collected biomarkers in the study subjects.

Additional details concerning statistical analyses will be included in the Statistical Analysis Plan (SAP) to be completed per Avid SOP.

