3.2. Sample Size Justification

No formal sample size calculation was performed. The study will stop enrolling subjects according to administrative consideration and decisions.

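### SAP 9.2 defines medical history by stop date, against its own listing and the protocol, so its coded summary table could omit stable ongoing conditions

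*SAP*

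**What the plan says.** SAP 9.2 gives the rule in one sentence: "Medical History findings are defined as those conditions which stop prior to or at Screening". It then specifies a listing for the safety population with start date, end date and a yes/no column, "Condition Still Present (Y/N". The section closes with the summary table: "Medical and Surgical History data will be presented by System Organ Class (SOC) and Preferred Term (PT), sorted in descending frequency". It does not say whether ongoing conditions are counted in that table.

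The protocol uses a different criterion. Section 7.7.2 reads: "Pre-existing conditions (i.e., undesirable experiences, signs or symptoms that begin prior to the Screening Visit) will be recorded on the medical history eCRF pages". The same section says that signs and symptoms attributed to such conditions "do not have to be recorded in the AEs section of the eCRF, unless there is an increase in frequency and severity". On output, protocol 8.1 commits to the following: "Subject listings of all data from the eCRFs as well as any derived variables will be presented".

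**The concern.** Medical history at baseline normally means whatever the subject brought into the study, resolved or not. The protocol collects it that way. The SAP sentence keeps only what was over by Screening, and no other SAP section takes up what was not. A programmer who follows the definition would tabulate resolved conditions only. One who follows the listing columns would tabulate everything. The two tables would differ, and the SAP does not say which is meant.

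What is at stake is the description of who was enrolled. Protocol 7.2 asks for a history that includes medical care for head trauma, and the study sets cognitively impaired fighters beside fighters without complaints. For a reader of the report, conditions still present are at least as informative as those that have ended.

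**Working it through.** The plan gives no figure here to reproduce, so the check sets the sections side by side.

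**1. The definition against its own listing.** Under SAP 9.2 a finding must have ended on or before Screening. Every qualifying row would then show No in the still-present column. A Yes can occur only for a condition that the definition shuts out. The sentence and the column cannot both do work.

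**2. The definition against the protocol.** Protocol 7.7.2 takes conditions that began before Screening. The SAP keeps the subset of these that also ended by Screening. The difference between the two sets is every condition ongoing at Screening.

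**3. Each kind of condition followed through the planned output, with the SAP rule applied literally.**

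| Condition | On history pages (protocol 7.7.2) | Finding under SAP 9.2 | SOC/PT history table | Subject listing | Adverse event output |
|---|---|---|---|---|---|
| Began before Screening, ended by Screening | Yes | Yes | Counted | Yes | No |
| Began before Screening, continues unchanged | Yes | No | Left out | Expected (protocol 8.1; still-present flag) | Not expected |
| Began before Screening, ongoing, increases after consent | Yes | No | Left out | Expected | May appear, as an adverse event |

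The second row is the gap: collected and expected in a listing, but in no coded summary.

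**4. The neighbouring section.** SAP 9.3 defines both prior medications (stopped before injection) and concomitant medications (including those still being taken at study end). SAP 9.2 has only the counterpart of the first category. No SAP section defines or tabulates ongoing conditions.

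**5. Where medical history is used.** It is not a factor in the two-way ANOVA for hypotheses 1 and 2, does not enter the Fisher tests for hypotheses 3 and 4, and is not among the correlates named in SAP 10.1.4. The adverse event and vital-sign sections do not draw on it either.

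**6. Size.** The number of ongoing conditions cannot be derived from the documents. As a scale, assume that the safety population equals the approximately 30 subjects planned. One subject is then 1/30 = 0.033. Each subject whose only record under a preferred term is an ongoing condition lowers that term's frequency by about 3.3 percentage points. The total effect runs from nothing, if no condition was ongoing, to the loss of every term recorded only as ongoing.

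**The case against.** The strongest reply is that the still-present column reveals the intent: nobody asks for that flag unless ongoing conditions are to be listed, so the definition is loose drafting that a sensible programmer would read past. The SAP also says that it should be read together with the protocol, whose onset rule is clear. This is a fair account of what was probably meant. It does not settle the SOC/PT table, because the only rule stated for what counts as a finding points the other way.

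A reader might go further and infer that ongoing conditions disappear from all output and would be reported as absent. The documents do not support that. Protocol 8.1 promises listings of all case report form data, and the SAP listing carries the flag. Conditions that increase can reach the adverse event pages. Partial information also appears elsewhere: SAP 9.1 tabulates the Beck Depression Inventory II and alcohol, tobacco and drug use; SAP 9.3 lists medications with their indication and whether they are ongoing; and SAP 9.5 tabulates brain volumes. Exclusion criterion 3 also bars current clinically significant cardiovascular disease. None of these is a coded summary of conditions, but together they rule out any claim of total loss.

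A reader might also infer that the comparison of impaired with normal fighters is compromised. It is not: no planned test uses medical history, and SAP 9.2 does not specify a split of its table by cognitive group.

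**Conclusion.** The concern holds in a narrow form. The stop-date sentence in SAP 9.2 is wrong as written, because it contradicts a column in its own section and the protocol's onset rule. Followed literally, it produces SOC/PT frequencies for resolved conditions only. The consequence is an incomplete baseline table, which makes this a minor point that is worth correcting.

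The conclusion rests on three assumptions: that the history pages were completed as protocol 7.7.2 directs, that the table is programmed from the SAP definition, and that no separate table specification overrides it. If the programmer counts everything on the history pages instead, the table is complete and only the wording is at fault.

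**What to change.** Replace the sentence in SAP 9.2 with: *Medical history findings are conditions that began prior to Screening, whether resolved or ongoing.* Take ongoing status from the flag already in the listing. If the table has been produced with a stop-date filter, remove the filter and rerun it.

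Separate rows or columns for resolved and ongoing conditions in the SOC/PT table would be a convenience. In a study of this size they are optional, since the listing already shows status by subject.

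The cost is one SAP sentence and at most one rerun of a descriptive table. The data are already on the medical history pages, and no other analysis changes.
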